**A COMPARISON OF METHODS OF DISCONTINUING NASAL CPAP IN PREMATURE INFANTS <30
WEEKS GESTATION – A FEASIBILITY STUDY**

NCT03292562

Version Date: 09/13/2017

A COMPARISON OF METHODS OF DISCONTINUING NASAL CPAP IN PREMATURE INFANTS <30 WEEKS GESTATION – A FEASIBILITY STUDY

[name]; [name]; [name]

Introduction: Nasal continuous positive airway pressure (NCPAP) mode of respiratory support is now widely used to support premature infants, especially those who are less than 30 weeks of gestation.¹⁻² Recently, three large studies have shown that NCPAP therapy initiated in the delivery room is equally effective as prophylactic surfactant in the treatment of respiratory distress syndrome (RDS).³⁻⁵ Additionally, volutrauma and atelectrauma have been implicated in the development of Bronchopulmonary dysplasia (BPD).⁶ Therefore, premature infants are being preferentially treated with NCPAP rather than mechanical ventilation. However, while there is significant body of literature justifying the use of NCPAP, very little is known about how long to continue CPAP and more importantly how and when to wean off NCPAP. There are three published trials, one of which showed, that infants are likely to tolerate being taken off NCPAP after gradual reduction in pressure with some increase in oxygen need.⁷ The second trial showed, that weaning from NCPAP to supplemental oxygen via high flow nasal cannula (HFNC) did not decrease duration of NCPAP therapy but, increased the duration of oxygen use.⁸ Another recent trial showed, that discontinuation of NCPAP, rather than cycling NCPAP, results in faster weaning off CPAP. In clinical practice, CPAP is either discontinued regardless of the pressure or, the pressure is gradually reduced before discontinuing CPAP based on individual physician preferences. However, a clinical trial comparing discontinuation of NCPAP with and without weaning the CPAP pressure has not been published. Therefore, this is a feasibility study comparing two strategies of discontinuing NCPAP.

Study question:

Among infants <30 weeks gestational age on NCPAP, does discontinuing CPAP after gradual reduction in CPAP pressure leads to successful weaning off CPAP when compared to discontinuing CPAP without weaning pressure.

P: Premature infants <30 weeks gestation requiring NCPAP therapy for respiratory support who are ready to wean NCPAP

I: Wean NCPAP pressure gradually before discontinuing NCPAP

C: Discontinue NCPAP without weaning pressure

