O: Number of total days on NCPAP after wean started or discontinuation, failure to wean off NCPAP, time to failure, need for intubation

T: 28 days after randomization

Study Population:

- Inclusion criteria:**

- All infants < 30 weeks by dates, on NCPAP therapy, on caffeine 10mg/kg daily
- Meet CPAP stability criteria for ≥ 12 hours
 - CPAP 6 cm H₂O
 - FiO₂ <= 0.25 and stable (to maintain sats 85-95%)
 - Respiratory rate consistently less than 60
 - Mild to no subcostal/intercostal retractions
 - No Apnea or bradycardia event that requires bag mask ventilation
 - Less than 3 apnea/brady/desat episodes in any 1 hour period for previous 6 hours.
 - Tolerated time off CPAP during routine CPAP care (~15 min)

- **Exclusion criteria:**
 - Major congenital anomalies including congenital heart disease
 - Anomalies that prevent discontinuation of NCPAP
 - Undergoing current evaluation for and/or treatment of sepsis

Allocation Plan: Blinding is not possible due to technological constraints. Subjects will be randomized using permuted blocks using 4-6-6 scheme. Assignment will be sequentially numbered and placed in opaque envelopes. Consent will be obtained in first 48hrs of life in potentially eligible patients. Subjects will be randomized once the subject meets eligibility (CPAP stability) criteria.

Interventions:

1. **Discontinue NCPAP after weaning pressures:** After randomization, CPAP pressure will be weaned by 1 every 24hours as long as the subjects continue to meet stability criteria after each wean, until CPAP of 4. If after decrease in CPAP pressure, the subject meets CPAP failure criteria (described below) pressure will be increased back to the previous level and after stabilization for 24 hours weaning process will be started again. Once the subject meets stability criteria on CPAP of 4, NCPAP will be stopped and subject will be placed on nasal cannula (NC) according to unit guidelines (max 1L flow, 30% FiO₂). Subjects will be considered to have failed CPAP discontinuation if they meet any one of the CPAP failure criteria after routine suctioning and prone positioning:
 - Respiratory rate >75 consistently
 - Respiratory distress defined as moderate-severe retractions, grunting, nasal flaring that persists for >30 min
 - FiO₂ >30% for 6 hours* (to keep oxygen saturations 85-95%)
 - Apnea or bradycardia that requires bag mask ventilation
 - >2 apnea/bradycardia episodes in 1 hourperiod

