Subjects will be restarted on CPAP of 6 and will be allowed to recover for 1 week. After 1 week, the weaning procedure will start again if the subject meets CPAP stability criteria.

2. **Discontinue NCPAP without weaning pressures:** After randomization, once the subject meets stability criteria, NCPAP will be stopped and subject will be placed on nasal cannula (NC) according to unit guidelines (max 1L flow, 30% FiO₂). Subjects will be considered to have failed CPAP discontinuation if they meet any one of the CPAP failure criteria as described before. Subjects will be restarted on CPAP of 6 and will be allowed to recover for 1 week. After 1 week, the weaning procedure will start again if the subject meets CPAP stability criteria.

End of study: Each patient will be followed for 28 days from randomization OR failure of CPAP wean x 2 attempts. Should patient need further escalation of care from CPAP, will be eligible to enter NIPPV study.

Outcomes: Primary outcome of interest is the number of days on NCPAP or mechanical ventilation from randomization until discharge (1 day= 0-24h). Secondary outcomes to be analyzed will be duration of endotracheal ventilation, failure to wean off NCPAP, rate of BPD, rate of NEC, time to full PO ad lib feeds, length of hospital stay, rate of air leak disorders.

Sample size calculation: This type of intervention has not been reported in literature as a result we have no prior data to help us determine the sample size. Therefore, this study will carried out in two phases. During the initial phase, the study will be carried out for 1 year. The data from the first phase will be used estimate the sample size for the subsequent definitive trial. The initial goal for enrollment is 50 patients.

Data analysis:

Baseline characteristics to be collected:

- Gestational age
- Birth weight
- Prenatal steroids
- Surfactant use
- Corrected gestational age at enrollment
- Weight at enrollment
- Duration of NCPAP before enrollment
- Duration of mechanical ventilation
- Co morbidities such as NEC, Sepsis episodes, IVH, treatment of PDA

Outcome indicators to be collected

- Total days on NCPAP since enrollment
- Total days on endotracheal ventilation since enrollment
- Time to wean off NCPAP
- Number of attempts
- Total days until full PO feeds
- Length of hospital stay

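### The primary outcome does not classify NIPPV days or give a rule for death, although infants who escalate from CPAP may enter a NIPPV study

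*Combined protocol and SAP*

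**What the plan says.** The combined protocol and SAP mentions NIPPV once, under End of study: "Should patient need further escalation of care from CPAP, will be eligible to enter NIPPV study". The Outcomes section that follows defines the primary outcome as the "number of days on NCPAP or mechanical ventilation from randomization until discharge". Mechanical ventilation is not defined. The next sentence uses a different term: "Secondary outcomes to be analyzed will be duration of endotracheal ventilation, failure to wean off NCPAP, rate of BPD".

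Other places bear on the same quantity:

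- **Study question, O and T.** The corresponding outcome is "Number of total days on NCPAP after wean started or discontinuation", with intubation listed separately and a time frame of "28 days after randomization".
- **End of study.** "Each patient will be followed for 28 days from randomization OR failure of CPAP wean x 2 attempts".
- **Outcome indicators to be collected.** The support durations listed are NCPAP days and endotracheal ventilation days, both from enrollment. The baseline list separately has NCPAP before enrollment and mechanical ventilation.
- **Statistical analysis plan.** A t-test for continuous variables if parametric criteria are met, and Kaplan-Meier or Cox methods for time to wean off NCPAP.

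Death is not an outcome, a collected item, a censoring event or an analysis rule anywhere in the document.

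**The concern.** A count of support days should rise when an infant does worse. If NIPPV days are left out, it can do the opposite: an infant whose condition requires more than CPAP leaves NCPAP, stops adding days, and can finish with a lower count than an infant who stays on NCPAP. Death on support raises the same problem. A count that runs to discharge has no defined value for an infant who dies first. The days accrued would be a short and apparently favourable result, while leaving the infant out would make the comparison conditional on survival.

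Two features raise the stakes. The Allocation Plan states that "Blinding is not possible due to technological constraints", so a rule left open now could be chosen later by people who know which arm it helps. The Sample size calculation section says first-phase data will be used to size the definitive trial, so the way these infants are scored affects the SD carried forward as well as the arm difference.

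**Working it through.** No figure in the plan depends on this point, so there is none to reproduce. The check is a comparison of the text, followed by an illustration.

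**1. Does the text classify NIPPV?** The Introduction says "premature infants are being preferentially treated with NCPAP rather than mechanical ventilation", which sets mechanical ventilation against NCPAP without placing NIPPV on either side. The primary outcome uses the broad term; the secondary outcome and the collected item use the endotracheal term. The Study question counts NCPAP only. These leave two readings open, and no sentence chooses between them.

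**2. Does the analysis fill the gap?** The t-test takes each infant's count as given. The survival analysis concerns time off NCPAP, a different quantity, and has no rule for a move to NIPPV or for death.

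**3. Effect on the arm difference.** From the documents: the goal of 50 infants and the 28-day period. Assumed: equal allocation (50/2 = 25 per arm), the NIPPV durations and numbers of infants, and the day of death. With total uncounted NIPPV days T in arms A and B:

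shift in difference of means = (T_A − T_B)/25

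- Equal totals: 0/25 = 0.
- One extra infant in one arm with 5 to 14 uncounted days: 5/25 = 0.20 to 14/25 = 0.56 day, in favour of that arm.
- Two infants with 5 days each in one arm (10 days), one infant with 14 days in the other: (14 − 10)/25 = 0.16 day, in favour of the arm with one infant.

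Direction therefore follows total days, not the number of infants. With unequal arms the shift is T_A/n_A − T_B/n_B, and equal totals no longer cancel exactly.

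**4. Death.** Suppose one infant dies on day 5 while on support, is scored at 5 days, and the window is 28 days. The arm mean is lower by between 0/25 = 0 and (28 − 5)/25 = 0.92 day, depending on how many of the other 23 days would have been on support. For a window running to discharge no upper limit can be given.

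**5. Effect on the SD.** Let an infant's full count be x, the arm mean m, the arm size n, and the uncounted days d. Replacing x by x − d changes the arm's sum of squares by

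d²(1 − 1/n) − 2d(x − m).

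This is negative when x − m exceeds d(1 − 1/n)/2. With n = 25, that threshold is 5 × 0.96/2 = 2.40 days for d = 5 and 14 × 0.96/2 = 6.72 days for d = 14. So if one infant in each arm loses the same d, the difference does not move, but the SD can rise or fall. If the affected infants are well above their arm mean it falls, and a definitive trial sized on it would be too small.

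**The case against.** The best reply is that mechanical ventilation was chosen as the broad term. It follows directly after the NIPPV sentence and gives way to a narrower term in the next one, so NIPPV may well be covered. That reading is possible, but the text does not state it and the outcome indicators do not provide NIPPV days with which to carry it out.

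Second, the NIPPV sentence is conditional and grants eligibility only. Escalation could mean intubation, which the outcome counts. If follow-up ends at the second failed wean, NIPPV may begin after it. This stands, and is why the window has to be settled first.

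Third, entry requires respiratory stability and excludes major anomalies and current sepsis evaluation or treatment, so deaths may be few; and this is a feasibility study with a goal of 50. Few deaths would limit the effect but would not supply a rule, and the data are meant to size the next trial.

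A reader might infer more than the documents support:

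- **That NIPPV days will be lost.** The list of indicators is not exhaustive: BPD and air leak are outcomes but are not on it either. The gap is an ambiguity.
- **That the arm with more escalations is favoured.** Step 3 of the working shows that total days decide, and that equal totals in equal arms cancel. A chance imbalance in one trial is also not systematic bias.
- **That the plan scores death as success.** It gives no score; the infant might be treated as missing.

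**Conclusion.** The point holds as a definitional gap in the primary outcome. The plan provides for escalation beyond CPAP but does not say whether NIPPV days count, does not list them for collection, and says nothing about death. Built from the listed indicators, the outcome can reward a worse course.

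The size cannot be determined, because no NIPPV or death rates are given. The figures of 0.20 to 0.56 day for one extra infant on NIPPV, and 0 to 0.92 day for one death on day 5, are illustrations resting on an assumed 25 per arm and assumed durations; only the goal of 50 and the 28 days come from the document. The between-arm effect may be zero. The effect on the SD remains possible even then. The change should be made, with medium confidence: it is cheap and is best settled before outcome data are seen by arm.

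**What to change.** 1. **Settle the window first.** Reconcile 28 days or two failed weans with follow-up to discharge. If counting stops at the second failure, later NIPPV is never observed.
2. **Define the outcome once.** Use the same wording in the Study question and Outcomes: days on any of NCPAP, NIPPV or endotracheal ventilation over that window. If the sponsor did not intend NIPPV to count, the plan should say so and explain why an infant who worsens onto it should stop accruing days.
3. **Collect what is needed.** Add NIPPV days, and death with its date, to the outcome indicators.
4. **Keep counting.** Infants who enter the NIPPV study stay in their randomized arm and continue to accrue support days.
5. **Give death an explicit score.** Report deaths by arm and prespecify one score, for example treating days from death to the end of the window as days on support, with observed days as a sensitivity analysis. That example needs a fixed window; it has no defined value if the count runs to discharge.

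The cost is a slightly broader endpoint if NIPPV was not meant to count, two chart items, one sensitivity analysis, and some further chart review for infants in the NIPPV study. No extra patients or procedures are needed.
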